9.7 Investigational Product Exposure and Treatment Compliance

Investigational product exposure and treatment compliance will be summarized by treatment group and overall for the All Randomized Set. The summary statistics will include:

- Subjects not dosed (n, % All Randomized)
- Subjects compliant with treatment (subjects swallowing all 16 capsules and the number of moxidectin capsules dispensed corresponds to the treatment assignment, n, % All Randomized)
- Subjects non-compliant with treatment:
 - Subjects with dosing errors (the number of moxidectin capsules does not correspond to the treatment assignment but the subject received 16 capsules overall, n, % All Randomized)
 - Subjects with dispensing errors (the number of capsules overall is not equal to 16, but the number of moxidectin capsules corresponds to the treatment assignment, n, % All Randomized)
 - Subjects with dosing and dispensing errors (the number of capsules overall is not equal to 16 and the number of moxidectin capsules does not match the treatment assignment, n, % All Randomized)
 - Subjects who did not swallow all 16 capsules (n, % All Randomized)

Study drug administration will be listed for the All Randomized Set.

9.8 Demographic and Baseline Characteristics

Descriptive summaries of demographic and baseline data will be presented by randomized treatment group and overall for all participants included in the FAS. Should the number of participants randomized but not receiving study drug support aggregate tables by randomized treatment group, these tables may be repeated for this subgroup of participants.

9.8.1 Baseline Demographic Characteristics

Descriptive statistics of demographic data will be reported for FAS subjects by randomized treatment group and overall:

- Age (years) (note: age is derived from year of birth per the formula described in the SAP Definitions Table),
- Age groups

- 18 to 64 (n, % FAS)
- ≥ 65 (n, % FAS)
- Sex (n, % FAS),
- Race (n, % FAS),
- Ethnicity (n, % FAS)
- Region
 - United States (n, % FAS)
 - Latin America (n, % FAS)
- Height at Screening (cm)
- Weight at Screening (kg)
- BMI at Screening (kg/m²) (note: BMI is derived from height and weight per the formula described in the SAP Definitions Table)
- BMI categories
 - Underweight (BMI < 18.5 kg/m²) (n, % FAS)
 - Healthy weight (≥ 18.5 kg/m², < 25 kg/m²) (n, % FAS)
 - Overweight (≥ 25 kg/m², < 30 kg/m²) (n, % FAS)
 - Obese (≥ 30 kg/m²) (n, % FAS)

Descriptive statistics may be repeated if the difference between the All Randomized Set and FAS support aggregate tables by randomized treatment group for this subgroup of subjects.

Additionally, the above demographic characteristics will be repeated and stratified by region, summarized by randomized treatment group and overall.

Demography will be listed for all subjects in the FAS.

9.8.2 Baseline Scabies Disease Characteristics

Descriptive statistics will be reported for the following scabies assessment characteristics at baseline (Day 0) for FAS subjects by randomized treatment group and overall:

- Number of lesions
- Scabies Severity:
 - Mild (≤ 10 lesions) (n, % FAS)
 - Moderate (11 to 49 lesions) (n, % FAS)
 - Severe (≥ 50 lesions) (n, % FAS)
- Diagnosed method
 - By microscopy (n, % FAS)
 - By dermoscopy (n, % FAS)

- Evidence of burrows (n, % FAS)
- Evidence of pruritus (n, % FAS)
- Evidence of nodules (n, % FAS)
- Evidence of mites (n, % FAS)
- Evidence of eggs (n, % FAS)
- Evidence of scybala (n, % FAS)
- Day 0 Method of assessment for mites, eggs, and scybala
 - Microscopy of skin scrapings (n, % FAS)
 - Dermoscopy (n, % FAS)
- Evidence of secondary bacterial infection (n, % FAS with secondary bacterial infection present)
- Number of body regions affected

Should the number of subjects randomized but not receiving study drug support aggregate tables by randomized treatment group, these tables may be repeated for this subgroup of subjects.

Additionally, the above scabies assessment characteristics will be repeated and stratified by region, summarized by randomized treatment group and overall.

Disease characteristics at Baseline and Day 28 will be listed.

9.9 Medical History

Medical history events will be coded using the latest Medical Dictionary for Regulatory Activities (MedDRA) version in place at the time of analysis. The version of MedDRA used will be indicated in the data summaries and listings.

The number and percentage of subjects with medical history events will be presented by system organ class (SOC), and preferred term (PT) in the All Randomized set, where SOC and PT will be presented in decreasing frequency of the total number of subjects with medical history events. The number and percentage of subjects with a history of any previous scabies infections will be included in the tabulation. The treatments used (permethrin cream, ivermectin or other) used by subjects with a prior history of scabies infection will be included in the tabulation. All events will be listed.

9.10 Prior and Concomitant Medications

Prior and concomitant medications will be coded using the World Health Organization Drug Dictionary (WHODD) and will be classified according to the default anatomical therapeutic chemical (ATC) code classification and PT. The version of WHODD used will be indicated in the data summaries and listings.

Prior medications are defined as medications with a stop date prior to the start of study drug administration. Prior medications should be entered on the 'Prior Medication' form of the eCRF. Medications that are ongoing at the administration of study drug or started after the time of administration of study drug will be deemed to be concomitant medications. If medication dates are incomplete and it is not clear whether the medication was concomitant, the medication will be assumed to be concomitant.

Prior and concomitant medications will be summarized separately in the same tabulation, displaying n (%) of FAS subjects for each dose group by ATC class and PT. Prior medications that are continuing at the start of the study (flagged as ‘ongoing’ or with a stop date after randomization) will be analyzed and reported in both the prior medications and concomitant medications categories. See Section 9.4.2 for additional detail.

Subjects may have more than one medication per ATC class and PT. At each level of subject summarization, a subject will be counted only once if one or more medications are reported by the subject at the same level. ATC class and PT will be presented in decreasing frequency of the total number of subjects with medications.

All prior and concomitant medications will be provided in line listings.

The collection of concomitant medications continuing, ending or starting during the extended safety follow-up to Week 16 will also be described.

9.11 Efficacy Analysis

9.11.1 Primary Efficacy Analyses: Superiority of Moxidectin to Placebo – Day 28 Complete Cure Rate

The three primary efficacy hypotheses to be tested are the comparison of the Day 28 Complete Cure rates (proportions) for each of three moxidectin dose groups to the placebo group adjusted for region. Each analysis will be conducted as a test of superiority for the marginal risk difference adjusted for region using the standardized estimator as outlined by [Steingrimsson et al \(2017\)](#). The standardized estimator estimates the average treatment effect using logistic regression with treatment group and region as main effects and Day 28 Complete Cure as the outcome variable. Predicted probabilities for Day 28 Complete Cure for each treatment group are generated for all FAS subjects regardless of their actual randomized treatment group but using their actual region values. The predicted probability of Day 28 Complete Cure for each treatment group across all subjects are then averaged and the difference in these averages is the standardized estimator for the marginal risk difference adjusted for region. The randomization seeds used to produce the analysis will be saved and documented to enable the results to be reproducible

Statistical significance will be based on a Dunnett adjusted two-tailed alpha level of 0.019 to account for the multiplicity of the three primary efficacy analyses and maintain a FWER of 0.05. For each comparison Wald type 95% CIs incorporating Dunnett’s critical value will also be calculated using the bootstrapped SE for the adjusted risk difference as suggested by [Steingrimsson et al \(2017\)](#). Should the bootstrap fail due to a small number of subjects in one of the two regions, the primary analysis will pool all subjects across regions (not adjust for region) and conduct the analysis using a Z-test for two independent proportions with pooled variance. Wald 95% CIs with unpooled variance incorporating Dunnett’s critical value will also be provided. These analyses will be conducted using the FAS.

As supportive analyses, the Day 28 Complete Cure rates for each moxidectin group and placebo, as well as the risk difference and 95% CIs for each pairwise comparison, will be calculated within each region. For these region subgroup analyses the proportion of index subjects achieving a Day 28 Complete cure for each randomized treatment group within region will be the unadjusted proportions with Wald 95% CIs for a single proportion. The 95% CI for the risk difference will be the Wald CIs for the difference between two independent proportions using the unpooled variance. Any significance test of the risk difference conducted within region will

be viewed as supportive and exploratory due to the potential lack of power. The 95% CIs and any hypothesis tests for these supportive analyses will not be adjusted for multiplicity.

See [Appendix 3](#) for specification of the logistic model and bootstrapping.

9.11.2 Handling of Missing Data for the Primary Analysis of Day 28 Complete Cure

For the Day 28 Complete Cure endpoint, subjects exposed to rescue medication (scabicides, including permethrin, ivermectin, benzyl benzoate, sulfur, lindane, crotamiton, malathion, tea tree oil, or spinosad) prior to the Day 28 assessment will be imputed as a non-responder. If a subject is exposed to a scabicide as a concomitant medication with an unknown start date, they will also be imputed as a non-responder unless the end date is known and is after Day 28. Additionally, subjects with missing Day 28 Complete Cure assessments due to missed visits or incomplete scabies assessments at Day 28 will also be imputed as non-responders. An exception would be if the missing Complete Cure endpoint was missing for reasons deemed as non-informative i.e. the Day 28 visit was missed because weather conditions prevented travel. For the non-informative missing data, the Complete Cure endpoint may be imputed via a fixed value using the methodology detailed in [Appendix 1](#). Should the missing data due to non-informative reasons be greater than 5% of the total sample size (approximately 200 subjects), a multiple imputation approach will be implemented, see [Appendix 2](#).

The determination of the use of rescue medication as well as informative vs non-informative missing data will be conducted prior to the blind break for the Day 42 analysis, see Section [9.6](#).

A subject line listing for subjects with imputed values for the primary efficacy endpoint will be provided. The line listing will include the randomized treatment group, the imputed value, observed value (if relevant), the reason for imputation (use of rescue medication, missed visit, incomplete scabies assessment etc.), and the type of imputation (non-responder, fixed value, multiple imputation). Note for any endpoint values imputed via multiple imputation the imputed value in the line listing will remain blank.

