Statistical significance will be based on a Dunnett adjusted two-tailed alpha level of 0.019 to account for the multiplicity of the three primary efficacy analyses and maintain a FWER of 0.05. For each comparison Wald type 95% confidence intervals incorporating Dunnett's critical value will also be calculated using the bootstrapped standard error (SE) for the adjusted risk difference as suggested by Steingrimsdottir *et al.* Should the bootstrap fail due to a small number of subjects in one of the two regions, the primary analysis will pool all subjects across regions (not adjust for region) and conduct the analysis using a Z-test for two independent proportions with pooled variance. Wald 95% confidence intervals with unpooled variance incorporating Dunnett's critical value will also be provided. These analyses will be conducted using the FAS.

As supportive analyses, the Day 28 Complete Cure rates for each moxidectin group and placebo as well as the RD and 95% CIs for each pairwise comparison, will be calculated within each region. Any significance tests of the risk difference conducted within region will be viewed as supportive and exploratory due to the potential lack of power.

The Day 28 Complete Cure status for subjects exposed to scabicides prior to their Day 28 assessment will be imputed as a non-responder (not cured) for the primary analyses using the FAS. Subjects missing Day 28 assessments due to events reasonably considered to be non-informative, i.e., SARS-CoV-2, will have their Day 28 Complete Cure rate imputed using multiple imputation (MI). Details of the imputation model and MI methods, as well as alternative approaches should the MI yield unreliable imputations due to overprediction or other issues, will be outlined in the SAP.

The estimand for each of the primary efficacy hypotheses outlined above is the comparison of the Day 28 Complete Cure rate of moxidectin without use of rescue medication versus the Day 28 Complete Cure rate of placebo without use of rescue medication. Rescue medication is defined as any scabicide, including permethrin, ivermectin, benzyl benzoate, sulfur, lindane, crotamiton, malathion, tea tree oil, or spinosad used between Day 0 and Day 28. Rescue medication does not include products used to manage the symptoms of scabies.

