4 SAMPLE SIZE DETERMINATION

Approximately 200 index subjects will be randomized into one of four cohorts using an equal allocation ratio. Only one subject will be enrolled per household; where more than one household member is screened for the study, the index subject is the youngest eligible member of the household.

The target sample sizes per randomized treatment group are shown in [Table 2](#). The sample size was selected to address the study's primary efficacy objective.

Table 2: Sample Size by Randomized Treatment Group

Randomized Treatment Group	Target Sample Size
Placebo	N = 50
Moxidectin 8 mg, single dose	N = 50
Moxidectin 16 mg, single dose	N = 50
Moxidectin 32 mg, single dose	N = 50

A sample size of 50 subjects per randomized treatment group will yield an approximate power of 75% for the pairwise comparisons of each moxidectin dose group to placebo assuming a placebo Day 28 Complete Cure rate of 40% or less and a moxidectin Day 28 Complete Cure rate of 70% or more. Power calculations for each pairwise comparison were conducted via a Z test for two independent proportions with pooled variance at a two-tailed adjusted alpha of 0.019. The pairwise adjusted alpha of 0.019 is used to control the familywise error rate (FWER) at an overall two-tailed alpha of 0.05 using a large sample approximation to Dunnett's critical value for the 3 pairwise comparisons of each moxidectin dose group to placebo.

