Across all subjects, regardless of treatment group, get the mean for each of the following variables:

1. Placebo_prob
2. Moxi8mg_prob
3. Moxi16mg_prob
4. Moxi32mg_prob

Step 6: Calculate the Standardized Risk Difference for each Pairwise Comparison Using the Average Predicted Probabilities calculated in Step 5.

5. Diff 8 vs Plb
6. Diff 16 vs Plb
7. Diff_32 vs Plb
8. Diff 16 vs 8
9. Diff 32 vs 16
10. Diff 32 vs 8

Step 7: Calculate the Bootstrapped SEs for the Average Predicted Probabilities in Step 5 and the Bootstrapped SEs for each pairwise Standardized Risk Difference calculated in Step 6.

- Bootstrap Step 1 through Step 6 1000 Times with Replacement.
- For 95% CIs for each the three pairwise comparisons against placebo use the relevant bootstrapped SE and the Z value corresponding to Dunnett's two-tailed adjusted alpha of 0.019
- For the 95% CI for each of the three pairwise comparisons comparing moxidectin groups use the relevant bootstrapped SE and the Z value corresponding to a two-tailed unadjusted alpha of 0.05

NOTE: The Process outlined in Steps 1 through 6 may be available in SAS using the "margins" statement in PROC GLIMMIX. See the following reference:

Wu, S. Computng Predictive Margins for Generalized Linear Models with PROC GLIMMIX, SAS Statistics Research and Applications, Paper #2022-03

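### At 50 subjects per arm the bootstrap Wald test with z = 2.3455 has a familywise error rate of about 5.4-5.8%, slightly above the 0.05 that the plan states

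*SAP*

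**What the plan says.** SAP 9.2 and 9.11.1, like Protocol 15.6.2, judge each of the three moxidectin-placebo comparisons at a two-tailed alpha of 0.019, to "account for the multiplicity of the three primary efficacy analyses and maintain a FWER of 0.05".

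SAP section 4 gives the source of 0.019: it controls the familywise rate "using a large sample approximation to Dunnett's critical value for the 3 pairwise comparisons". The same section states the test used for planning: "Power calculations for each pairwise comparison were conducted via a Z test for two independent proportions with pooled variance".

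The primary analysis is a different procedure. It fits a logistic model with treatment and region, standardizes to a marginal risk difference, and forms intervals "using the bootstrapped standard error (SE) for the adjusted risk difference" (Protocol 15.6.2; SAP 9.11.1 agrees). SAP Appendix 3 Step 7 draws 1000 bootstrap samples with replacement, states no stratification of the resampling, and for the comparisons with placebo says to "use the relevant bootstrapped SE and the Z value corresponding to" alpha 0.019. Appendix 2 Step 7, for the multiple-imputation branch, states Wald tests and intervals with that same Z. The pooled-variance Z-test returns only as a fallback, if the bootstrap fails because one region is small.

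**The concern.** The error-rate statement is attached to a procedure other than the one for which power was calculated. A bootstrapped standard error of a difference in proportions behaves like the unpooled standard error: it shrinks when the observed arm rates happen to differ, which is when a false positive is in play. It is then referred to a normal quantile, although each arm has only 50 subjects. Both features push the test towards rejecting too often. Neither document gives a small-sample correction or a type I error check.

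All three primary claims, and the Dunnett-adjusted 95% intervals, rest on the stated familywise rate. A dose that only just crosses the threshold could be challenged on this ground.

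**Working it through.** **Inputs.** From the SAP: 50 per arm, four arms at 1:1:1:1, stratified by two regions (sections 4 and 5.1); alpha 0.019 (section 4); 1000 bootstrap samples (Appendix 3); design rates "assuming a placebo Day 28 Complete Cure rate of 40% or less and a moxidectin Day 28 Complete Cure rate of 70% or more" (section 4). Assumed: per-arm region splits of 10/40, 25/25 and 5/45. The documents give no split, only that one region is expected to be small (SAP 1.2).

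**Step 1: reproduce the plan's figures.**
- z for two-tailed 0.019 is 2.3455.
- Pooled SE under the null: mean rate 0.55; sqrt(2 x 0.55 x 0.45 / 50) = 0.0995.
- SE under the alternative: sqrt((0.40 x 0.60 + 0.70 x 0.30) / 50) = 0.0949.
- Power: Phi((0.30 - 2.3455 x 0.0995) / 0.0949) = Phi(0.70) = 75.9%. The plan says about 75%, so it reproduces.
- Large-sample two-sided Dunnett value for three comparisons with correlation 0.5: 2.3490, alpha 0.0188, which rounds to 0.019. Using 0.019 gives an asymptotic familywise rate of 5.04%, so rounding adds only about 0.04 points.

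**Step 2: why the two standard errors differ.** With equal arms of size n and observed difference d, the pooled variance equals the unpooled variance plus d²/(2n). At 40% and 70% that is 0.0090 + 0.09/100 = 0.0099. The unpooled ratio is therefore always the larger whenever d is not zero.

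**Step 3: exact enumeration without region.** Four Binomial(50, p) arms with a common p; the familywise rate is the probability that any of three |z| exceeds 2.3455.

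| Common cure rate | Pooled Z | Unpooled Wald |
|---|---|---|
| 10% | 4.3% | 5.1% |
| 15% | 4.6% | 6.0% |
| 20% | 4.7% | 6.1% |
| 30% | 4.9% | 5.8% |
| 40% | 5.0% | 5.5% |
| 50% | 5.6% | 5.6% |

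**Step 4: simulate Appendix 3.** Logistic model with treatment and region, standardized risk difference, 1000 unstratified resamples of 200 subjects, rejection when |RD / bootstrapped SE| > 2.3455. There were 40,000 or 100,000 trials per scenario; the Monte Carlo SE is 0.07-0.12 points.

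| Cure rate under the null | Split per arm | Familywise rate | In moxidectin's favour |
|---|---|---|---|
| 10% | 10/40 | 4.8% | 2.3% |
| 15% | 10/40 | 5.5% | 2.7% |
| 20% | 10/40 | 5.5% | 2.6% |
| 30% | 10/40 | 5.8% | 2.8% |
| 40% | 10/40 | 5.5%, 5.6% (two runs) | 2.7% |
| 40% | 25/25 | 5.5% | 2.8% |
| 40% | 5/45 | 5.4% | 2.7% |
| 50% | 10/40 | 5.7% | 2.9% |
| 30% and 45% by region | 10/40 | 5.8% | 2.9% |
| 25% and 43.75% by region | 10/40 | 5.6% | 2.9% |

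**Step 5: intervals.** When all true differences are zero, simultaneous coverage is one minus the familywise rate. For 5.4-5.8% that is 94.2-94.6%.

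**Step 6: what corrects it.** The unrounded 2.349 leaves 5.6% at 40% cure. The Dunnett t value on 196 df, 2.367, leaves about 5.3-5.4%. The critical value that gives 5% at 40% cure is about 2.40-2.41. Adding the factor sqrt(50/49) = 1.0102 makes the effective threshold 2.367 x 1.0102 = 2.391. This gives about 5.0-5.2% at 30-40% cure and about 5.4-5.5% at 50%.

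**The case against.** The plan openly calls its critical value a large-sample approximation, and half a point of drift is ordinary for such a method in a Phase 2 dose-ranging trial. In the direction that matters the excess is only 0.1-0.4 points over 2.5%. It could change a conclusion only for a p-value just under 0.019, while the trial is designed around 40% against 70%. All of this stands, and it limits the weight of the point.

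Outside the multiple-imputation branch, the SAP assigns the bootstrapped SE and Z to the intervals and does not spell out the test statistic. That the test is the same ratio is an inference from 9.11.1 and Appendix 3 Step 7. It is a strong one: no other SE is defined for the adjusted estimator, and Appendix 2 states the Wald test. The slight under-coverage does not depend on it. If the bootstrap fails and the pooled Z-test takes over, the rate at 40% cure is 5.0% and the concern largely disappears.

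A reader might infer an error rate of 6% or more from the enumeration in Step 3. Those values belong to the plain unpooled Wald test at 15-20% cure. The Appendix 3 bootstrap, resampling the whole trial, lets arm sizes vary, which raises the SE slightly and gives 5.5% at those rates. A reader might also blame the rounding to 0.019, but Step 1 shows that this is immaterial.

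**Conclusion.** The stated familywise rate of 0.05 is slightly exceeded. With the procedure as written and 50 per arm, it is about 5.4-5.8% for common cure rates of 15-50%, including 5.4-5.6% at the plan's own 40% placebo rate. The cause is an unpooled bootstrapped SE used with a normal quantile.

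The documents do not support the stronger reading that error control is lost or that the primary results would be invalid. The excess is small, is absent at about 10% cure, and bears only on a borderline dose.

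The result rests on reading the main-branch test as the Wald ratio, on unstratified resampling, and on assumed region splits and region differences. The rate changed little across those tried.

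**What to change.** Keep the standardized estimator. In SAP 9.2, 9.11.1, Appendix 2 Step 7 and Appendix 3 Step 7, for both the tests and the intervals against placebo:

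- multiply the bootstrapped SE by sqrt(n/(n-1)), with n the arm size, and use the finite-sample Dunnett value 2.367 (together about 2.39-2.40 on the uncorrected SE);
- state that the primary test is this Wald ratio;
- say that familywise control is approximate.

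This is a calibration and not an exact repair: at 50% cure, discreteness keeps the rate near 5.4-5.5%.

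The cost is SAP wording and two constants in the program. Power at 40% against 70% falls by roughly one point or less (77.6% to 77.3% in the region-adjusted calculation) and stays above the stated 75%. SAP 1.1 allows an amendment with a rationale before unblinding for the Day 42 analysis; after that, the change would have to be reported as a deviation.

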10 INVESTIGATIONAL PRODUCT

10.1 Randomization Process

A unique screening number will be sequentially allocated to each subject who provides written informed consent. Subjects who fail screening and are approved to be rescreened will retain their original screening number.

Subject eligibility will be confirmed before randomization. On Day 0, eligible subjects will be randomized using an Interactive Response Technology (IRT) system and assigned a unique Subject Number. The unblinded pharmacist at each site will dispense the IP corresponding to the assigned Subject Number.

Within the IRT system, the randomization of subjects to treatment will be stratified by region (e.g., US and Latin America). Within each region, a permuted block randomization algorithm reflecting an equal allocation ratio among the 4 treatment cohorts of 1:1:1:1 will be derived. The algorithm within each region will be independent and may consist of randomly varying block sizes. Block sizes will not be revealed to sites or Sponsor personnel involved in the conduct of the study. The algorithm will be generated by an unblinded statistician who is otherwise independent of the study. The random selection will be stratified by region and treatment and performed using the IRT system.

Approximately 200 subjects will be randomized targeting a sample size of 50 subjects per cohort across regions. A subset of approximately 20 subjects will be randomly selected from each arm to provide sparse blood samples for PK analyses. To ensure the study drug allocation remains blinded, subjects from all arms of the study will be sampled. Further details on the randomization procedure, treatment dispensing, and accountability are provided in the SRM.

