1.2 Changes to Protocol Planned Analyses

The following changes have been made to the planned analyses described in the clinical study protocol MDGH-MOX-2002 Version 3 dated 28 Dec 2023:

- The description of the process for randomization, described under Section 10.1 of the current study protocol, was updated in this SAP Section 5.1. Instead of a unique screening number, a site specific sequential Subject Number was allocated to each subject who provided written informed consent. This Subject Number was used throughout the study to identify the subject. A unique Randomization Number was assigned to the subject upon randomization and this randomization number was only recorded on the Randomization electronic case report form (eCRF) page. Study drug was dispensed according to the Randomization Number, not according to the Subject Number.
- Two additional sensitivity analyses have been included to support the primary efficacy analysis:
 - A Completers Analysis excluding subjects with missing data for the primary endpoint with the exception of subjects exposed to scabicides.
 - An analysis that adjusts for Baseline lesion count as the sole covariate, other than randomized treatment group.
- The protocol states that sensitivity analyses will be conducted to assess the impact of missing data on the results. As such, a tipping point analysis has been included in the SAP.
- A repeat of the primary analysis within each Region will not be conducted due to anticipated small sample size within one of the Regions. However, descriptive analyses of the primary efficacy endpoint stratified by Region will be provided.

- Exploratory pairwise comparisons between each of the moxidectin dose groups have been added.
- For the non-informative missing data, the Complete Cure endpoint may be imputed via a fixed value using the methodology detailed in [Appendix 1](#). Should the missing data due to non-informative reasons be 5% of the total sample size, (approximately 200 subjects), a multiple imputation (MI) approach will be implemented using the methodology detailed in [Appendix 2](#).
- The following additional exploratory endpoints have been included in this SAP that are not otherwise listed in the current study protocol:
 - The Day 28 Complete Cure without regards to pruritus.
 - The proportion of index subjects achieving clearance for each individual component of the Complete Cure endpoint

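### The switch from the region-adjusted primary test to an unadjusted Z-test depends on an undefined bootstrap failure that can be judged only after unblinding

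*SAP*

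**What the plan says.** Protocol 10.1 states that "the randomization of subjects to treatment will be stratified by region", and SAP 5.1 confirms it. SAP 9.11.1 fits a logistic model with treatment and region, averages the predicted probabilities to obtain a marginal risk difference, and tests it with a bootstrapped standard error. The threshold is explicit: "Statistical significance will be based on a Dunnett adjusted two-tailed alpha level of 0.019".

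The escape clause follows: "Should the bootstrap fail due to a small number of subjects in one of the two regions, the primary analysis will pool all subjects". Region is then dropped from the analysis, and a pooled-variance Z-test takes its place. Dunnett's critical value is kept for the intervals. Protocol 15.6.2 has the same clause.

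The bootstrap instruction in SAP Appendix 3, Step 7 is short: "Bootstrap Step 1 through Step 6 1000 Times with Replacement". It names no strata, no convergence rule, no tolerated share of bad replicates and no minimum region size. SAP 9.11.3.2 (tipping point) refers to the same switch but attributes it to small treatment groups within strata, which is a different condition from a small region.

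The sponsor expects the situation to arise. SAP 1.2 drops the repeat of the primary analysis within region "due to anticipated small sample size within one of the Regions". Protocol 5.4.3 sets no regional quotas. SAP 9.11.2 dates the decisions on rescue use and missing-data class before the Day 42 blind break; nothing dates this one.

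**The concern.** The bootstrap refits a model that contains treatment group, so whether it failed can be seen only by someone who holds the treatment codes and, in practice, both results. A replicate in which the small region has one outcome produces a separation warning. One analyst may call that a failure and switch tests. Another may note that the estimate is finite and carry on. The SAP supports either reading. What is at stake is which of two tests is primary, and whether the randomization stratum stays in the analysis.

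**Working it through.** **Inputs.** 200 subjects, 50 per arm; two-sided pairwise alpha 0.019 (SAP 9.11.1); planning rates "assuming a placebo Day 28 Complete Cure rate of 40% or less and a moxidectin Day 28 Complete Cure rate of 70% or more" (SAP 4); 1000 replicates (Appendix 3). Assumed: small-region size m, because no document gives it; free resampling, because Appendix 3 names no strata; overall cure rate (40 + 70 + 70 + 70)/4 = 62.5%.

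**The plan's own figure.** Power was "conducted via a Z test for two independent proportions with pooled variance". With 50 per arm, 40% versus 70% and alpha 0.019 this gives 75.9%, against about 75% stated. The large-sample Dunnett critical value for three comparisons is 2.349, a pairwise alpha of 0.0188. Both reproduce.

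**Degenerate replicates.** Call a replicate degenerate if the small region (m subjects, c cured) is absent or shows one outcome only. Under free resampling:

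P = (1 − c/200)^200 + (1 − (m − c)/200)^200 − (1 − m/200)^200, and P(at least one in 1000) = 1 − (1 − P)^1000.

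For m = 20, c = 12: 0.94^200 + 0.96^200 − 0.90^200 ≈ 0.000289, so 1 − (1 − 0.000289)^1000 = 25%.

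| m | c | P per replicate | At least one in 1000 | Same, averaged over binomial c |
|---|---|---|---|---|
| 8 | 5 | 5.5% | 100% | 100% |
| 12 | 8 | 1.8% | 100% | 99.8% |
| 16 | 10 | 0.23% | 90% | 82% |
| 20 | 12 | 0.029% | 25% | 50% |
| 30 | 19 | 0.0012% | 1.2% | 9% |
| 40 | 25 | 0.00002% | below 0.1% | 1% |

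Under multiple imputation (Appendix 2) there are 50 × 1000 = 50,000 replicates. At m = 20 about 50,000 × 0.000289 ≈ 14 degenerate ones are expected.

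**The two wordings differ in practice.** If the 9.11.3.2 wording is read as an empty treatment-by-region cell, at least one such replicate is near certain up to m = 25 and has probability 85% at m = 30. The region wording gives 1.2-9% at m = 30. An empty cell does not by itself break a main-effects model.

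**Does a degenerate replicate spoil the bootstrap?** With one outcome in the region, its fitted probabilities go to 0 or 1 and the risk difference stays finite. If the region is absent, the estimate reduces to the unadjusted difference. In a simulation of Appendix 3 (300 draws per trial, 4000-8000 trials, m = 8 to 20, region effect 0 or −1.5 on the logit scale), the standard error without degenerate replicates was 0.997-1.000 times the one with them.

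**Does the choice of test matter?** Per comparison at 40% versus 70%:

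| m, region effect | Adjusted bootstrap | Pooled Z | Better of the two | Disagree |
|---|---|---|---|---|
| 12, 0 | 77.5% | 76.8% | 78.0% | 1.8% |
| 12, −1.5 | 76.8% | 75.4% | 77.2% | 2.2% |
| 20, −1.5 | 76.0% | 74.1% | 76.4% | 2.7% |

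A further simulation gave 3.4% disagreement at m = 40. The 1.8% with no region effect shows that part of the disagreement comes from the variance (bootstrap against pooled null), not from region.

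Under the null (m = 8 to 20), familywise error was 5.4-6.1% for the adjusted bootstrap, 4.0-5.1% for the Z-test and 5.6-6.2% for the better of the two (Monte Carlo standard error 0.3-0.4 points). With a prognostic region, the Z-test's pairwise error was 1.76% at m = 8 and 1.52% at m = 20, against 1.9%.

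**The case against.** The best defence is that the fallback is not improvised. Protocol and SAP both pre-specify it, it uses the Full Analysis Set, it keeps Dunnett's critical value, and it is the test on which the sample size rests. Its trigger is tied to a small region, seeds are saved, and deviations must be justified in the study report. All of this stands, and it limits the harm. It does not say what counts as failure or when that is decided.

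Three stronger readings are tempting, and the documents do not support them.

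- **Failure is almost certain.** That needs a small region of about 12 or fewer of 200 subjects. SAP 1.2 anticipates a small region but gives no number. A degenerate replicate is also not a failed bootstrap.
- **Free resampling is a stated choice.** It is the plain reading of silence in Appendix 3; SAP 9.11.1 also refers to a cited methods paper for the bootstrapped standard error.
- **Resampling within region-by-arm cells cures the problem.** At m = 12, with plausible outcome patterns, 62-96% of trials would still have at least one degenerate replicate. Cell resampling also shrank the standard error by 1-2% without better error control.

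**Conclusion.** The gap is real and its effect is modest. The trigger for changing the primary test is undefined, worded in two ways, and visible only after unblinding, although the SAP protects comparable decisions by dating them before the blind break.

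A reader might infer that the sponsor could materially inflate error by choosing the better result. The numbers do not bear that out: choosing the better of the two tests adds about 0.1 points of familywise error over the adjusted bootstrap, and about 1-2 points over the Z-test. The tests disagree in roughly 2-3% of comparisons at the planning rates, and the fallback is conservative when region is prognostic.

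These sizes rest on assumed regions of 8 to 40 subjects, the planning cure rates, and assumed region effects of 0 and −1.5 on the logit scale. The case for acting is that the choice of primary test should not be open once results can be seen, and closing it costs almost nothing.

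**What to change.** Amend the SAP before the Day 42 blind break:

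1. **Decide on blinded counts.** State a minimum number of subjects in the smaller region, and choose the primary test from the region counts before treatment codes are released. Remove bootstrap behaviour as the trigger.
2. **Say how awkward replicates are handled.** Keep single-outcome replicates, since the risk difference stays finite, and state the rule for a replicate with the region absent. Name the resampling strata. Resampling within region removes absent-region replicates; region-by-arm cells are optional and not sufficient alone.
3. **Keep region in the fallback.** Replace the unadjusted Z-test with a region-stratified test using a null (Cochran-Mantel-Haenszel type) variance, which retains the randomization stratum and holds the 0.019 level. A Mantel-Haenszel risk-difference test with its standard unpooled variance is not a good substitute: in simulation it ran at 2.3-2.5% against 1.9%.
4. **Align the text.** Give SAP 9.11.1, 9.11.3.2 and Appendix 3 the same condition, and carry the bootstrap rules into Appendix 2, Step 5.

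The cost is minor SAP wording and programming, with no new data and no effect on subjects.
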